15.3 Data Analysis

The analyses will be conducted on all participant data when the trial ends. Data will be presented by treatment group and overall.

Categorical variables will be summarized by frequency distributions (number and percentages of subjects) and continuous variables will be summarized by descriptive statistics (mean, standard deviation etc). Adverse events will be summarized by treatment group using the Medical Dictionary for Regulatory Activities (MedDRA) system organ class and preferred term. Separate tabulations will be produced for all treatment-emergent AEs (TEAEs), treatment-related AEs (those considered by the Investigator as at least possibly drug

related), SAEs, discontinuations due to AEs, and AEs ≥Grade 3 severity. By-subject listings will be provided for any deaths, SAEs, and AEs leading to discontinuation.

Descriptive statistics for each treatment group will be provided for clinical laboratory values (e.g., hematology, serum chemistry, and urinalysis) and vital signs data, presented as both actual values and changes from baseline relative to each on-study evaluation. Abnormal clinical laboratory values will be listed.

All data will be provided in by-subject listings.

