15.4.2 Adverse Events

All adverse events (AEs) recorded during the study through the date of randomization through 28 days after the last dose of study drug will analyzed.

All AE's will be coded according to MEDRA and summarized using SOC and Preferred term.

AE's will be summarized using incidence rates. Therefore, each subject will only contribute once for a given adverse event SOC or PT.

A summary of the incidence of any adverse event, SAE, and adverse events leading to discontinuation will be presented. Summaries will display, by treatment group, the incidence of patients with events, the frequency of patients with events within each primary system organ class and by preferred terms. For each preferred term and each system organ class a patient will be counted only once. For summaries on severe or drug-related AE, for a given patient, the highest severity or relationship for a specific preferred term will be considered.

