16.5 Evaluating AEs and SAEs

16.5.1 Severity Rating

The severity of an adverse event (AE and SAE) is to be scored according to the following scale:

Mild Awareness of sign or symptom, but easily tolerated

Moderate Discomfort enough to cause interference with usual

activity

Severe Incapacitating with inability to work or perform usual

activity

An AE that is assessed as severe should not be confused with a SAE. An event is defined as 'serious' when it meets one of the pre-defined outcomes as described in Section16.2 "Definition of a SAE".

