#### 4 5 2 Adverse Events

Adverse events will be analyzed in terms of treatment-emergent adverse events (TEAEs) which are defined as any AEs that begin or worsen on or after the start of study drug through 28 days after the last dose of study drug.

A treatment-related TEAE is defined as a TEAE that was considered by the Investigator to be at least possibly related to the study drugs.

If a subject experiences the same AE more than once with different toxicity grades, the event with the highest grade will be tabulated in the "by grade" tables. If a subject experiences multiple AEs under the same preferred term (SOC), the subject will be counted only once for that preferred term (SOC). In addition, AEs with a missing severity will be presented in the summary table as an intensity category of "Missing."

An overall summary table presenting the number of subjects who experienced the following will be presented by treatment arm: any TEAE, any related TEAE, any Grade 3 or 4 TEAE, any related Grade 3 or 4 TEAE, any serious TEAE, any serious related TEAE, any TEAE leading to discontinuation of treatment, any TEAE leading to study discontinuation, and any TEAE leading to death.

The incidence of TEAEs will be summarized by MedDRA SOC and preferred term. Tables summarizing the incidence of TEAEs will be generated for each of the following:

- x All TEAEs
- **X** TEAEs reported as treatment-related
- x Severe or Grade 3/4 TEAEs
- x Related Grade 3/4 TEAEs
- **▼** Serious TEAEs
- Related Serious TEAEs

If no subjects experience any of the events in the overall summary table, the corresponding table by SOC and preferred term will not be produced.

No formal hypothesis-testing analysis of AE incidence rates will be performed.

All AEs occurring on-study will be listed in subject data listings.

By-subject listings also will be provided for the following: subject deaths, serious AEs, and AEs leading to withdrawal.

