#### Table 14.3.1.1

# Overall Summary of Treatment-Emergent Adverse Events (Safety Population)

		B244		
	Statistic	(N=xx)	Placebo (N=xx)	(N=xx)
Subjects with at Least 1 Treatment-Emergent Adverse Event (TEAE)	n (%)	xx (xx.x)	xx (xx.x)	xx (xx.x)
Subjects with at Least 1 Treatment-Related TEAE	n (응)	xx (xx.x)	xx (xx.x)	xx (xx.x)
Subjects with at Least 1 Grade 3 or 4 TEAE	n (%)	xx (xx.x)	xx (xx.x)	xx (xx.x)
Subjects with at Least 1 Treatment-Related Grade 3 or 4 TEAE	n (응)	xx (xx.x)	xx (xx.x)	xx (xx.x)
Subjects with at Least 1 Serious TEAE	n (응)	xx (xx.x)	xx (xx.x)	xx (xx.x)
Subjects with at Least 1 Treatment-Related Serious TEAE	n (%)	xx (xx.x)	xx (xx.x)	xx (xx.x)
Subjects with at Least 1 TEAE that led to Treatment Discontinuation	n (%)	xx (xx.x)	xx (xx.x)	xx (xx.x)
Subjects with at Least 1 TEAE that led to Study Discontinuation	n (%)	xx (xx.x)	xx (xx.x)	xx (xx.x)
Subjects with 1 TEAE that led to Death				

If a subject experiences multiple occurrences in the category of Adverse event , the subject will be counted only once for that

PT/SOC.

If a subject experiences the same AE more than once with different CTCAE grades, the event with the highest grade will be tabulated.

TEAE is defined as any AEs that begin or worsen on or after the start of study drug through 30 days after the last dose of study drug.

Treatment-related TEAE is defined as TEAE that was considered by the Investigator to be at least possibly related to the study drug.

Severity will be graded based on the NCI CTCAE, Version 4.03.

Adverse events are coded using MedDRA v20.0.

Source: DIMMINIT

AOBiome Therapeutics Confidential Protocol ADB244-001

Page 1 of x

DATE: HH:MM/DDMMMYYYY

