# Table 14.3.1.2

Treatment-Emergent Adverse Events (TEAE) by MedDRA System Organ Class and Preferred Term (Safety Population)

System Organ Class		B244	Placebo	Overall	
Preferred Term	Statistic	(N=xx)	(N=xx)	(N=xx)	
Any TEAE	n (%)	xx (xx.x)	xx (xx.x)	xx (xx.x)	
System Organ Class 1					
Preferred Term 1		xx (xx.x)	xx (xx.x)	xx (xx.x)	
Preferred Term 2	n (응)	xx (xx.x)	xx (xx.x)	xx (xx.x)	
Etc.	n (%)	xx (xx.x)	xx (xx.x)	xx (xx.x)	
System Organ Class 2					
Preferred Term 1	n (%)	xx (xx.x)	xx (xx.x)	xx (xx.x)	
Preferred Term 2	n (%)	xx (xx.x)	xx (xx.x)	xx (xx.x)	
Etc.	n (%)	xx (xx.x)	xx (xx.x)	xx (xx.x)	
Etc.					

TEAE is defined as any AEs that begin or worsen on or after the start of study drug through 30 days after the last dose of study drug. If a subject experiences multiple occurrences in the same PT/SOC, the subject will be counted only once for that PT/SOC.

48

Adverse events are coded using MedDRA v20.0.

Source: ZLMWLQQQ

Repeat Table 14.3.1.2 for the following tables:

Table 14.3.1.3 Treatment-Related Treatment-Emergent Adverse Events (TEAE) by MedDRA System Organ Class and Preferred Term (Safety Population)

PROGRAMMING NOTE: filter for at least possibly related to the study drug. Add footnote "Treatment-related TEAE is defined as TEAE that was considered by the Investigator to be at least possibly related to the study drug."

Table 14.3.1.4 Grade 3 or 4 Treatment-Emergent Adverse Events (TEAE) by MedDRA System Organ Class and Preferred Term (Safety Population)

PROGRAMMING NOTE: filter for grade = 3 or 4. Add footnote "Severity will be graded based on the NCI CTCAE, Version 4.03." AND "If a subject experiences the same AE more than once with different CTCAE grades, the event with the highest grade will be tabulated."

Table 14.3.1.5 Treatment-Related Grade 3 or 4 Treatment-Emergent Adverse Events (TEAE) by MedDRA System Organ Class and Preferred Term (Safety Population)

PROGRAMMING NOTE: filter for grade = 3 or 4 and at least possibly related to the study drug. Add footnote "Treatment-related TEAE is defined as TEAE that was considered by the Investigator to be at least possibly related to the study drug." AND "Severity will be graded based on the NCI CTCAE, Version 4.03." AND "If a subject experiences the same AE more than once with different CTCAE grades, the event with the highest grade will be tabulated."

Table 14.3.1.6 Serious Treatment-Emergent Adverse Events (TEAE) by MedDRA System Organ Class and Preferred Term (Safety Population)

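### Adverse event severity is scored Mild/Moderate/Severe in the protocol but tabulated as Grade 3 or 4 under CTCAE v4.03 in the SAP, with no mapping between the two

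*SAP*

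**What the plan says.** Protocol 16.5.1 gives the only severity instruction to investigators: "The severity of an adverse event (AE and SAE) is to be scored according to the following scale". Three levels follow: Mild, Moderate and Severe, defined by how well the event is tolerated and how far it interferes with activity. The top level, Severe, reads "Incapacitating with inability to work or perform usual" activity. The section contains no numeric grade and does not mention CTCAE.

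The protocol's analysis text is mixed. Section 15.3 lists a separate tabulation of "AEs ≥Grade 3 severity". Section 15.4.2 returns to words: "For summaries on severe or drug-related AE, for a given patient, the highest severity or relationship for a specific preferred term will be considered".

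The SAP works mainly in grades. Section 4.5.2 puts any Grade 3 or 4 TEAE and any related Grade 3 or 4 TEAE in the overall summary, although its list of by-SOC/PT tables has an entry that sets Severe beside Grade 3/4. The shell for Table 14.3.1.1 carries the footnote "Severity will be graded based on the NCI CTCAE, Version 4.03". The instruction for Table 14.3.1.4 is "PROGRAMMING NOTE: filter for grade = 3 or 4", and Table 14.3.1.5 adds relatedness to the same filter; both repeat the CTCAE footnote. Listing 16.2.7.1 has that footnote too, under a combined severity and grade column whose first entry pairs Mild with Grade 1.

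Section 4.5.2 also says that if no subject has a given event in the overall summary, "the corresponding table by SOC and preferred term will not be produced". SAP Section 5, on changes to planned analyses, does not mention severity grading.

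**The concern.** Safety and tolerability are the primary objective, and adverse events are the stated safety endpoint. The Grade 3 or 4 rows and tables are the SAP's only tabulated view of severity. As written, they depend on a graded variable that the protocol's severity instruction does not create.

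Two things could go wrong. A programmer who applies the filter literally to three-level data would report no severe events and then, under the SAP's own rule, leave out the tables that would have shown them. A programmer who converts Severe to Grade 3 on personal judgement would produce usable counts, but under a footnote that credits them to a grading system the investigators were not told to use. A reader of the study report could not tell which had happened.

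**Working it through.** No sample size, error rate or event count enters this point, so there is nothing numeric to reproduce. The check sets the texts side by side and follows the SAP filter through each possible content of the severity field.

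**Step 1. The scale in each place**

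| Place | Scale used |
|---|---|
| Protocol 16.5.1 (scoring instruction) | Mild / Moderate / Severe |
| Protocol 15.3 (planned tabulation) | Grade 3 or higher, no grading system named |
| Protocol 15.4.2 (AE summaries) | Severe, highest severity |
| SAP 4.5.2, overall summary | Grade 3 or 4 |
| SAP 4.5.2, table list | Severe set beside Grade 3/4 |
| SAP Tables 14.3.1.1, 14.3.1.4, 14.3.1.5 | Grade 3 or 4, CTCAE v4.03 |
| SAP Listing 16.2.7.1 | Word and grade paired (Mild with Grade 1 visible), CTCAE v4.03 |

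No row supplies a rule that turns the words into grades. The protocol's category is also open-ended (3 or higher), while the SAP's stops at 4.

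**Step 2. The filter under each possible field content**

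- *A. The field holds only the three words and no conversion is programmed.* No record has grade 3 or 4. The two rows in Table 14.3.1.1 read zero, and the suppression rule in SAP 4.5.2 removes Tables 14.3.1.4 and 14.3.1.5.
- *B. The words are converted in order: Mild = 1, Moderate = 2, Severe = 3.* This extends the one pairing visible in the listing shell and is an assumption. The filter then selects exactly the Severe events. The scale has three levels, so Grade 4 has no source category. The counts are those of Severe events as Protocol 16.5.1 defines them, and the CTCAE footnote misdescribes how they were graded. The same holds if the field carries a word and a grade but the level was chosen by the 16.5.1 definitions.
- *C. The eCRF captures CTCAE v4.03 grades.* The filter and the footnotes are right. Protocol 16.5.1 then does not describe what was collected, and SAP Section 5 is silent on the change.

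In each case at least one statement in the documents is wrong or missing.

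**Step 3. Reach**

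- Table 14.3.1.1 has 9 rows; 2 use Grade 3 or 4, so 9 − 2 = 7 do not depend on severity.
- Tables 14.3.1.2 to 14.3.1.7 are 6 by-SOC/PT tables; 2 (14.3.1.4 and 14.3.1.5) use the filter, so 6 − 2 = 4 do not.
- Listing 16.2.7.1 is repeated as Tables 14.3.2.1, 14.3.2.2 and 14.3.2.3, so the severity column and its footnote appear in 1 + 3 = 4 outputs.
- Counts of all TEAEs, related TEAEs, serious TEAEs, discontinuations and deaths do not use severity and are unchanged.

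**The case against.** The best defence is that the intended meaning can be recovered. SAP 4.5.2 names Severe next to Grade 3/4 when it lists the table, and the listing shell pairs Mild with Grade 1. A sensible programmer would infer that Severe belongs in the table, so the empty-table outcome requires someone to overlook both cues. Every on-study event is also listed with its severity, so a severe event would stay visible somewhere. The grade language is not an invention of the SAP either: Protocol 15.3 already asks for events of Grade 3 or higher, and what the SAP adds is the upper limit of 4 and the CTCAE version.

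Most of this stands, and it limits the point. It makes outcome B more likely than outcome A, and it places the inconsistency inside the protocol as well as between the two documents. It does not supply a mapping rule, a source for Grade 4, or support for the CTCAE footnote if the three-level scale was used.

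Three stronger readings are tempting and are not supported:

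- That CTCAE grades were never collected. The eCRF is not among the documents. The listing column is broken in the extracted text, and what remains is compatible with a field holding both word and grade.
- That all severe events will be lost. This follows only under outcome A.
- That Severe on the protocol scale differs from CTCAE Grade 3. Neither document reproduces the CTCAE definitions, so the comparison cannot be made from them.

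**Conclusion.** The inconsistency is real and should be corrected. The protocol's scoring instruction uses three words; Protocol 15.3 and the SAP report grades; the SAP attributes the grades to CTCAE v4.03; no mapping is stated; Grade 4 has no counterpart on the protocol scale; and SAP Section 5 does not record a change.

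Its reach is moderate: two rows of the overall summary, two by-SOC/PT tables, and the severity column and footnote of the event listing with its three repeats. These outputs serve the primary objective, but no hypothesis test of event rates is planned and the main event counts are untouched. How much would go wrong depends on a fact outside the documents, namely what the eCRF severity field contains. With words only and no conversion, the severity tables vanish. With an undocumented conversion, the counts can be used but the description of the grading is wrong. With true CTCAE grades, the tables work and the protocol is the document to reconcile.

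**What to change.** First confirm what the eCRF severity field captures. Then use that one scale everywhere.

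- *If it is the Protocol 16.5.1 scale:* replace Grade 3 or 4 with Severe in SAP 4.5.2, in the two rows of Table 14.3.1.1, and in the titles and filters of Tables 14.3.1.4 and 14.3.1.5. Reword the toxicity-grade sentence in SAP 4.5.2 to refer to highest severity. Delete the CTCAE v4.03 footnotes and those on differing CTCAE grades wherever they occur, including Listing 16.2.7.1 and its repeats, and drop the grade half of the listing's severity column. In Protocol 15.3, change Grade 3 or higher to Severe.
- *If CTCAE grades are captured:* keep the SAP outputs, reconcile Protocol 16.5.1 with what investigators recorded, align the open-ended category in Protocol 15.3 with the SAP's 3 or 4, and record the change of scale in SAP Section 5.

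The first route costs only wording and shell edits, with no new data. The second needs a protocol correction and a Section 5 entry.

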# Table 14.3.1.2

Treatment-Emergent Adverse Events (TEAE) by MedDRA System Organ Class and Preferred Term (Safety Population)

System Organ Class		B244	Placebo	Overall	
Preferred Term	Statistic	(N=xx)	(N=xx)	(N=xx)	
Any TEAE	n (%)	xx (xx.x)	xx (xx.x)	xx (xx.x)	
System Organ Class 1					
Preferred Term 1		xx (xx.x)	xx (xx.x)	xx (xx.x)	
Preferred Term 2	n (응)	xx (xx.x)	xx (xx.x)	xx (xx.x)	
Etc.	n (%)	xx (xx.x)	xx (xx.x)	xx (xx.x)	
System Organ Class 2					
Preferred Term 1	n (%)	xx (xx.x)	xx (xx.x)	xx (xx.x)	
Preferred Term 2	n (%)	xx (xx.x)	xx (xx.x)	xx (xx.x)	
Etc.	n (%)	xx (xx.x)	xx (xx.x)	xx (xx.x)	
Etc.					

TEAE is defined as any AEs that begin or worsen on or after the start of study drug through 30 days after the last dose of study drug. If a subject experiences multiple occurrences in the same PT/SOC, the subject will be counted only once for that PT/SOC.

48

Adverse events are coded using MedDRA v20.0.

Source: ZLMWLQQQ

Repeat Table 14.3.1.2 for the following tables:

Table 14.3.1.3 Treatment-Related Treatment-Emergent Adverse Events (TEAE) by MedDRA System Organ Class and Preferred Term (Safety Population)

PROGRAMMING NOTE: filter for at least possibly related to the study drug. Add footnote "Treatment-related TEAE is defined as TEAE that was considered by the Investigator to be at least possibly related to the study drug."

Table 14.3.1.4 Grade 3 or 4 Treatment-Emergent Adverse Events (TEAE) by MedDRA System Organ Class and Preferred Term (Safety Population)

PROGRAMMING NOTE: filter for grade = 3 or 4. Add footnote "Severity will be graded based on the NCI CTCAE, Version 4.03." AND "If a subject experiences the same AE more than once with different CTCAE grades, the event with the highest grade will be tabulated."

Table 14.3.1.5 Treatment-Related Grade 3 or 4 Treatment-Emergent Adverse Events (TEAE) by MedDRA System Organ Class and Preferred Term (Safety Population)

PROGRAMMING NOTE: filter for grade = 3 or 4 and at least possibly related to the study drug. Add footnote "Treatment-related TEAE is defined as TEAE that was considered by the Investigator to be at least possibly related to the study drug." AND "Severity will be graded based on the NCI CTCAE, Version 4.03." AND "If a subject experiences the same AE more than once with different CTCAE grades, the event with the highest grade will be tabulated."

Table 14.3.1.6 Serious Treatment-Emergent Adverse Events (TEAE) by MedDRA System Organ Class and Preferred Term (Safety Population)

PROGRAMMING NOTE: filter for SERIOUS = YES.

Table 14.3.1.7 Treatment-Related Serious Treatment-Emergent Adverse Events (TEAE) by MedDRA System Organ Class and Preferred Term (Safety Population)

PROGRAMMING NOTE: filter for SERIOUS = YES and at least possibly related to the study drug. Add footnote "Treatment-related TEAE is defined as TEAE that was considered by the Investigator to be at least possibly related to the study drug."

Repeat Listing 16.2.7.1 for the below table listings.

Table 14.3.2.1 Serious Adverse Events

PROGRAMMING NOTE: filter for SERIOUS = YES and remove Serious Column.

Table 14.3.2.2 Adverse Events Leading to Early Discontinuation

PROGRAMMING NOTE: filter for subjects who discontinued early.

Table 14.3.2.3 Subject Deaths

PROGRAMMING NOTE: filter for subject deaths, remove Outcome column and accompanying footnote and renumber other footnotes accordingly.

Confidential

Page 1 of x

DATE: HH:MM/DDMMMYYYY

Table 14.3.3.1

Summary of Values and Change from Baseline for Hematology Parameters (Safety Population)

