7.3 Study Withdrawal and Withdrawal From Investigational Product and Stopping Criteria

A participant may withdraw from the study at any time at his/her own request, or may be withdrawn at any time at the discretion of the Investigator.

Reasons for withdrawal (participants who refuse to complete any remaining study visits) or discontinuation (participants who prematurely stop the application) at any time during the study may include, but are not limited, to the following:

- For safety reasons, either at the discretion of the Investigator or at the participant's request
- For protocol violations at the discretion of AOBiome
- Due to concomitant therapy that could interfere with the results of the study (the Investigator will report all such information on the CRFs and decide, in accordance with AOBiome, whether the participant is to be withdrawn).

The reason for participant study withdrawal will be recorded in the electronic Case Report Form (eCRF). Data from participants withdrawing from the study will be considered evaluable up to the point at which they are withdrawn using the same criteria for evaluability as for participants who complete the study.

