15.4.4 Adverse Events leading to treatment discontinuation

Adverse events leading to treatment discontinuation will be summarized overall and by primary system organ class and preferred term.

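### The SAP listing of AEs leading to discontinuation selects subjects rather than events, and the SOC/PT summary required by Protocol 15.4.4 is not among the planned outputs

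*SAP*

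**What the plan says.** **The listing.** In the SAP notes that follow the Table 14.3.1.2 shell, one output is named "Table 14.3.2.2 Adverse Events Leading to Early Discontinuation". Its format is set by "Repeat Listing 16.2.7.1 for the below table listings", so it is a by-subject listing and not an incidence table. Its selection rule is "PROGRAMMING NOTE: filter for subjects who discontinued early".

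**What the protocol asks for.** Section 15.3 states: "By-subject listings will be provided for any deaths, SAEs, and AEs leading to discontinuation". Section 15.4.2 adds: "A summary of the incidence of any adverse event, SAE, and adverse events leading to discontinuation will be presented". Section 15.4.4 is the most specific: "Adverse events leading to treatment discontinuation will be summarized overall and by primary system organ class and preferred term".

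**What the SAP text plans.** Section 4.5.2 describes the by-subject listing in causal terms, as events that led to withdrawal. It also plans an overall by-arm summary (Table 14.3.1.1), with one row for TEAEs that led to treatment discontinuation and another for TEAEs that led to study discontinuation. For the breakdown by event type it says "Tables summarizing the incidence of TEAEs will be generated for each of the following" and names six sets: all, related, severe or Grade 3/4, related Grade 3/4, serious, and related serious.

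**The concern.** Safety and tolerability are the primary objective of this trial, and the AEs that make people give up a topical product are a central part of that result. A reader of the study report will look for two things: which events caused stopping, and what kinds of event they were in each arm.

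The output whose title answers the first question is selected on a different criterion from its title. No planned output answers the second. The disposition shell (Table 14.1.1) does not help as a cross-check: its reasons for early study discontinuation are death, loss to follow-up, consent withdrawal, investigator's decision and other, with no category for an adverse event.

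**Working it through.** The plan gives no figure on this point, so the check is a comparison of texts.

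**Step 1: is the filter at subject level or event level?** The note names subjects and mentions neither causality nor action taken. The note for the neighbouring Table 14.3.2.1 selects on the seriousness flag of the event, so the SAP does use event-level filters where it means them. The title of Table 14.3.2.2, SAP 4.5.2 and Protocol 15.3 are all causal. The note is the exception.

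**Step 2: what would the note select?** The word discontinued has two meanings in these documents. Protocol 7.3 separates withdrawal (refusing the remaining visits) from "discontinuation (participants who prematurely stop the application" and so on, which is stopping the product. Protocol 7.5 and the SAP disposition shell use the word for leaving the study. Under Protocol 13.3 a completer has attended every visit up to Day 42. The cases are:

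| Event | Belongs under the title? | Listed if discontinued = stopped product | Listed if discontinued = left study |
|---|---|---|---|
| AE that caused both stopping the product and leaving | Yes | Yes | Yes |
| Unrelated AE in a subject who stopped the product and left for another reason | No | Yes | Yes |
| Unrelated AE in a subject who finished 28 days of product but missed Day 42 | No | No | Yes |
| AE that caused stopping the product in a subject who attended through Day 42 | Yes | Yes | No |

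Over-inclusion (row 2) occurs on either reading. Under-inclusion (row 4) occurs only on the study reading, and the note does not say which applies.

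**Step 3: could the right filter be applied?** Yes. The source, Listing 16.2.7.1, carries an action-taken field with a code for drug stopped and a column for discontinuation from the study. The second header is broken in the extracted text; I read it as an event-level column.

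**Step 4: is the SOC/PT summary anywhere else?** The six sets in SAP 4.5.2 correspond to Tables 14.3.1.2 to 14.3.1.7, and none concerns discontinuation. SAP 4.5.2 also says that when an event in the overall summary does not occur, its matching SOC/PT table will be dropped. That presumes a matching table, yet the two discontinuation rows of Table 14.3.1.1 have none.

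**Step 5: is the omission declared?** SAP 1.1.2 says the SAP will set out where it departs from the protocol. Section 5 declares two changes: the per-protocol definition and the deferral of biomarker and microbial data. This one is not there.

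**Step 6: what is unaffected?** The two rows of Table 14.3.1.1 are defined by what the TEAE led to, and nothing ties them to the filter of Table 14.3.2.2. SAP 4.5.2 also commits to listing every on-study AE.

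**The case against.** The strongest reply is that little is at risk. Table 14.3.1.1 already gives event-caused treatment and study discontinuations by arm, which meets the overall half of Protocol 15.4.4. Table 14.3.2.2 is a listing and inherits the action-taken and study-discontinuation columns, so a careful reader can separate causal from non-causal rows. A product stop in a subject who completes follow-up still appears in Listing 16.2.7.1, with its SOC and PT. On the Protocol 7.3 meaning, such a subject would be selected anyway. Finally, the note sits under a causal title and may be loose shorthand.

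Most of this stands, and it sets the limits of the point. A reader might infer that tolerability as a whole is misreported, or that AE-driven product stops are lost. The documents support neither, because the by-arm counts are correctly defined and the full AE listing retains the events.

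The reply leaves three things unanswered. Programmers work from the note, and followed as written it puts non-causal events under a causal label. Row-by-row inspection of Table 14.3.2.2 cannot recover events that the filter has left out. Being able to compile the SOC/PT breakdown by hand from a listing is not the by-arm summary that the protocol commits to.

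**Conclusion.** The point holds in a limited form. The listing is mis-selected for its label: over-inclusive on either reading, and also under-inclusive if discontinued means leaving the study. The SOC/PT summary of AEs leading to treatment discontinuation is absent and its absence is undeclared. The size is one listing and one missing table. No efficacy result and no overall AE count changes.

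Two further inferences should be resisted. A reader might apply the 20% dropout allowance to the 130 planned subjects (130 × 0.20 = 26) and say that 26 subjects will be wrongly listed. The 20% is a sample-size allowance. The 26 would include leavers with no AE, who would not appear, and leavers who stopped because of an AE, who belong there. The documents give neither proportion, so the number of misplaced rows cannot be estimated from them. A reader might also count subjects who leave because they need rescue treatment as non-AE leavers. Protocol 8.14 links rescue to worsening of the treated disease, and Protocol 16.1 gives worsening of a pre-existing condition as an example of an AE, so some of these may be genuine AE-led discontinuations.

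The conclusion assumes that the note would be programmed literally and that the fields in Listing 16.2.7.1 are recorded for each event.

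**What to change.** 1. Replace the subject-level note for Table 14.3.2.2 with an event-level filter: keep an AE if its action taken is drug stopped, or if it is marked as leading to discontinuation from the study. Label the two kinds separately, so that the treatment-emergent events can be reconciled with the two rows of Table 14.3.1.1.
2. Repeat the Table 14.3.1.2 shell for TEAEs leading to treatment discontinuation, by SOC, PT and arm, and add it to the list in SAP 4.5.2, as Protocol 15.4.4 requires. If the sponsor decides against the table, section 5 of the SAP should declare that as a change from the protocol.

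The cost is one changed filter and one repeat of an existing shell. No new data collection is needed if the fields are recorded for each event, as the listing shell indicates.
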